8.3.6 Events of Special Interest	Clarified that major adverse cardiovascular and cerebrovascular events includes cerebrovascular accident and transient ischemic attack, non-fatal myocardial infarction or unstable angina, cardiovascular death.	Improved the clarity of the definitions for events that qualify as adverse events of special interest.
	• Clarified that for infections, only those that are serious, opportunistic, or fungal are included as adverse events of interest.	
9.3.3 Secondary Endpoints and Estimands	Updated the method of handling missing data for the secondary endpoint of percentage of subjects who experience flare from non-response imputation (NRI) to multiple imputation.	The multiple imputation analysis method better represents missing data than NRI. The number of subjects with missing data may be larger than the number of subjects who experience a flare, so using NRI may result in an analysis dominated by missing data.
9.5 Sample Size Determination	Updated the power calculation for Part B to align with the primary endpoint of HiSCR75.	Corrected power calculation in Part B in line with HiSCR75, which was inadvertently missed in the previous amendment when the primary endpoint was updated from HiSCR to HiSCR75.
Global	Minor editorial and document formatting revisions.	Administrative change.
Global	Version and date were revised on the title page and in the header throughout the document.	Administrative change.

Table of Contents

Protocol Summary	
Synopsis	
Schema	
Schedule of Activities for Part A and Part B	1
Introduction	1
Study Rationale	
Background	
Disease Background	1
IL-17	
Izokibep Background	2
Benefit/Risk Assessment	2
Risk Assessment	2
Benefit Assessment	2
Overall Benefit-Risk Conclusion.	2
COVID-19 Benefit/Risk Assessment	2
Objectives, Endpoints, and Estimands	2
Study Design	
Overall Design	
Part A: Single-arm, Open-label	
Part B: Randomized, Double-blind, Dose-finding	
Independent Data Monitoring Committee	
Number of Sites	
Number of Subjects.	3
Study Duration for Subjects	3
Scientific Rationale for Study Design.	3
Justification for Dose	
End of Study Definition	3
Study Population	3
Inclusion Criteria	3
Exclusion Criteria	3
Lifestyle Considerations	4
Screen Failures.	
Criteria for Temporarily Delaying	
COVID-19 Related Precautions	4
Study Drug(s) and Concomitant Therapy	4
Study Drug(s) Administered	
Dosage, Administration and Schedule	
Preparation, Handling, Storage, and Accountability	

1.1. Synopsis

Protocol Title: A Phase 2b Pivotal Study to Evaluate the Efficacy and Safety of Izokibep in Subjects with Moderate to Severe Hidradenitis Suppurativa

Brief Title: Hidradenitis Suppurativa Phase 2b Pivotal Study of Izokibep

Rationale:

Izokibep is a small protein molecule that acts as a selective, potent inhibitor of interleukin 17A (IL-17A), to which it binds with high affinity. This study investigates izokibep in subjects with moderate to severe hidradenitis suppurativa (HS) and is intended to be one of 2 adequate and well-controlled studies to support a claim of efficacy of izokibep in subjects with HS.

Overall Design:

This is a phase 2b pivotal, multi-center, dose-finding study to evaluate the efficacy, safety, and immunogenicity of izokibep in subjects with moderate to severe HS. Subjects must have HS lesions present in ≥ 2 distinct anatomic areas, one of which is Hurley Stage II or Hurley Stage III and a total abscess and inflammatory nodule count of ≥ 5 . Subjects with draining fistula count of ≥ 20 at screening will be excluded.

This study consists of 2 parts. Part A is an exploratory open-label, single-arm investigation in which a minimum of 20 and up to 30 subjects will be enrolled. Once Part A is fully enrolled, subsequent subjects will be enrolled into Part B. Part B is a randomized, double-blind, placebo-controlled, parallel-group, dose-finding investigation in which approximately 170 subjects will be enrolled.

This study will be conducted at study sites in North America and Europe. Additional sites and regions may be added.

Objectives and Endpoints

Objectives	Endpoints								
Primary									
Part A									
 To explore the efficacy of izokibep as measured by HiSCR75¹ at Week 12 	HiSCR75 ¹ at Week 12								
Part B									
To demonstrate that one or both treatment regimens of izokibep is efficacious compared to placebo, as measured by HiSCR75 ¹ at Week 16	HiSCR75 ¹ at Week 16								
Secondary									
Part A									
To explore the safety and tolerability	TEAEs and SAEs								
	Laboratory values and vital signs at collected timepoints								
To explore the immunogenicity of izokibep as measured by the presence of ADAs	• ADAs								
Part B									
To demonstrate that one or both regimens of izokibep is efficacious, as measured by:									
 Percentage of subjects achieving HiSCR90¹ at Week 16 	 HiSCR90¹ at Week 16 HiSCR100¹ at Week 16 								
 Percentage of subjects achieving HiSCR100¹ at Week 16 	HiSCR50¹ at Week 16								
 Percentage of subjects achieving HiSCR50¹ at Week 16 									
 Percentage of subjects who experience ≥ 1 disease flare through 16 weeks of treatment² 	HS flares through Week 16								
 Percentage of subjects with baseline Hurley Stage II who achieve AN count of 0, 1, or 2 at Week 16 	AN count of 0, 1, or 2 at Week 16								

Objectives	Endpoints
• Percentage of subjects achieving at least 3-point reduction from baseline in NRS in Patient Global Assessment of Skin Pain at its worst at Week 16 among subjects with baseline NRS ≥4	NRS in Patient Global Assessment of Skin Pain at its worst at Week 16
To assess the safety and tolerability of izokibep as measured by the incidence of TEAEs, events of interest, SAEs, and clinically significant laboratory values and vital signs	 TEAEs, events of interest, and SAEs Laboratory values and vital signs at collected timepoints
To assess the immunogenicity of izokibep as measured by the presence of ADAs	• ADAs

ADAs = anti-drug antibodies; AN = abscess and inflammatory nodule; HiSCR = hidradenitis suppurativa clinical response; HS = hidradenitis suppurativa; IHS4 = International Hidradenitis Suppurativa Severity Score; NRS = numeric rating scale; SAE = Serious Adverse Event; TEAE = treatment-emergent adverse event ¹ HiSCR50/75/90/100 is defined as at least a 50%, 75%, 90%, or 100% reduction from baseline in the total AN count, with no increase from baseline in abscess or draining fistula count.

Brief Summary:

Overall, approximately 200 subjects with moderate to severe HS will be enrolled.

Part A is an open-label, single-arm, investigation consisting of up to a 28-day screening period, a 31-week treatment period and a follow-up period that includes 2 visits to be completed by all subjects at Week 39 and Week 45. For subjects who early terminate, the follow-up visits should be completed 8 weeks (\pm 5 days) and 14 weeks (\pm 5 days) after the last dose of study drug. A minimum of 20 subjects and up to 30 subjects meeting eligibility criteria will be enrolled into Part A (Group 0). Subjects will be assigned to treatment with open-label izokibep subcutaneous (SC) 160 mg every week (QW) from Day 1/Week 0 to Week 31. Once enrollment in Part A has finished, enrollment will begin into Part B.

Part B is a randomized, double-blind, placebo-controlled, parallel-group, dose-finding investigation to evaluate the efficacy, safety, and immunogenicity of izokibep in subjects with moderate to severe HS. Subjects will complete up to a 28-day screening period, followed by a 16-week double-blind treatment period. At completion of the Week 16 visit procedures, subjects randomized to placebo will be switched to active treatment in a blinded manner for the Week 16 dose through Week 30 (Q2W dose group) or Week 31 (QW dose group). Subjects randomized to izokibep will remain on the same dose through Week 30 (Q2W dose group) or Week 31 (QW dose group). After their respective treatment periods, all subjects will enter a follow-up period that includes 2 visits to be completed at Week 39 and Week 45. For subjects who early terminate, the follow-up visits should be completed 8 weeks (± 5 days) and 14 weeks (± 5 days) after the last dose of study drug.

² Flare is defined as ≥ 25% increase in AN count with a minimum increase of 2 AN relative to baseline.

In Part B, approximately 170 subjects will be randomized into 1 of 4 groups in a 1:1:2:2 ratio as follows:

- Group 1 (n = 28-29): placebo SC QW from Day 1 (Week 0) to Week 15, then izokibep SC 160 mg QW from Week 16 to Week 31.
- Group 2 (n = 28-29): placebo SC every other week (Q2W) from Day 1 (Week 0) to Week 14, then izokibep SC 160 mg Q2W from Week 16 to Week 30.
- Group 3 (n = 56-57): izokibep SC 160 mg QW from Day 1 (Week 0) to Week 31.
- Group 4 (n = 56-57): izokibep SC 160 mg Q2W from Day 1 (Week 0) to Week 30.

Randomization will be stratified by any prior biologic/Janus Kinase (JAK) inhibitor use for HS (Yes/No) and Hurley Stage (II or III).

Subjects will complete study assessments according to the study visits outlined in the Schedule of Assessments. Day 1 corresponds to the first dose of study drug. All visits will be scheduled based on the Day 1 visit.

The primary endpoint will be assessed at Week 16 in Part B only. The last dose of study drug will be administered on Week 31 for QW dosing groups and at Week 30 for Q2W dosing groups.

Number of Subjects:

Approximately 200 subjects will be enrolled in the study.

Study Drug Groups and Duration:

- Group 0 (n = minimum 20 subjects and up to 30 subjects): izokibep SC 160 mg QW from Day 1/Week 0 to Week 31.
- Group 1 (n = 28-29): placebo SC QW from Day 1 (Week 0) to Week 15, then izokibep SC 160 mg QW from Week 16 to Week 31.
- Group 2 (n = 28-29): placebo SC every other week (Q2W) from Day 1 (Week 0) to Week 14, then izokibep SC 160 mg Q2W from Week 16 to Week 30.
- Group 3 (n = 56-57): izokibep SC 160 mg QW from Day 1 (Week 0) to Week 31.
- Group 4 (n = 56-57): izokibep SC 160 mg Q2W from Day 1 (Week 0) to Week 30.

Study drug doses are fixed and will not be adjusted for individual subjects during the study. Subjects assigned to placebo SC QW and placebo SC Q2W will be grouped together into a single placebo group for comparison to each dosing regimen of izokibep for Part B.

Data Monitoring/Other Committee

An independent Data Monitoring Committee (DMC) will be established to monitor data on an ongoing basis to ensure the continuing safety of the subjects enrolled in this study.

The DMC will consist of at least one medical expert with the relevant therapeutic area expertise and at least one statistician. The DMC will also have a minimum of 3 members, one of whom will serve as the Chair. The DMC responsibilities, authorities, and procedures will be documented in the DMC charter. The committee will meet approximately every 6 months to review interim data. After each review, the DMC will make recommendations regarding the continuation of the study based on safety.

Part A

The DMC will review data in Part A, after all subjects have had the opportunity to complete the Week 8 visit (or discontinued the study early). Based on this review, the DMC may recommend continuing, stopping, or altering Part B.

Part B

In Part B, no formal interim analysis is planned for the purpose of stopping or altering this study. The DMC will review unblinded data when the first approximately 105 subjects randomized into Part B have had the opportunity to complete the Week 8 visit to make a recommendation on further development activities for izokibep. The DMC will not be empowered to recommend stopping this study or changing the sample size due to a demonstration of positive efficacy. The type I error rate for hypothesis tests at the end of the study will be decreased by 0.0001 to account for this interim summary of unblinded data. The study team and the investigators will remain blinded to these interim results until after the study is completed. After all subjects have had the opportunity to complete the Week 16 assessment in Part B, the analysis of the primary endpoint may be completed. Site staff and all members of the study team who interact with site staff will remain blinded to individual subject treatment assignment until all subjects have completed all visits in the study.

[figure not shown]
Statistical Considerations

Data from Parts A and B will be summarized separately. Objectives and statistical hypotheses will be addressed using data from Part B only. The treatment policy estimand will be used in general for efficacy data, with all treated subjects contributing to Part A and all randomized subjects contributing to Part B. All treated subjects will contribute to safety analyses in both Parts A and B.

For comparisons of izokibep to placebo in Part B, the 2 dosing regimens of izokibep (QW and Q2W) will be compared separately to placebo. The 2 placebo dosing regimens (QW and Q2W) will be combined for comparison to each izokibep dosing regimen. Binary endpoints including the primary endpoint of HiSCR rate will be compared with a stratified test of risk difference. Continuous endpoints will be compared with a repeated measures mixed model.

Safety data will be summarized separately for Part A and Part B. Adverse events, serious adverse events, and laboratory data will be summarized.

1.2. Schema

 $EOS = end\ of\ study;\ FU = follow-up;\ QW = once\ weekly;\ Q2W = every\ other\ weekly;$

^a Randomization will be stratified by any prior biologic/Janus Kinase (JAK) inhibitor use for hidradenitis suppurativa (Yes/No) and Hurley Stage (II or III).

^b Two follow-up visits will be completed by all subjects at Week 39 (± 5 days) and Week 45 (± 5 days). For subjects who early terminate, the follow-up visits should be completed at 8 weeks (± 5 days) and 14 weeks (± 5 days) after the last dose of study drug.

1.3. Schedule of Activities for Part A and Part B

																			Follo	ow-up ^b
Procedures	Screen Treatment Period (weeks) ^a												ı	Ī	ı		8 weeks after last dose	14 weeks after last dose/EOS		
	≤ 28 d prior to d1	0 (d1)	1	2	3ª	4	8	12	13ª	14	15ª	16	17ª	18	20	24	28	32 or ET ^p	39	45
Informed consent	X																			
Eligibility criteria	X	X																		
Hurley staging	X	X										X								
Demography	X																			
Physical exam	X																	X		
Weight	X	X																		
Height	X																			
Medical and medication history	X	X																		
Alcohol and nicotine use	X																			
Vital signs ^c	X	X	X	X	X	X	X	X	X	X	X	X	X	X	X	X	X	X	X	
12-lead ECG ^d	X											X						X	X	
Chest X-ray ^e	X																			
C-SSRS	X	X				X	X	X				X			X	X	X	X	X	
AE reporting ^f (through 4 weeks after last dose)		_																	-	
SAE reporting ^f (through 8 weeks after last dose)	X	_																	—	

																			Follo	ow-up ^b
Procedures	Screen		Treatment Period (weeks) ^a												8 weeks after last dose	14 weeks after last dose/EOS				
	≤ 28 d prior to d1	0 (d1)	1	2	3ª	4	8	12	13ª	14	15ª	16	17ª	18	20	24	28	32 or ET ^p	39	45
Prior & Concomitant medication ^g	Х	_																	-	
Efficacy Assessments																				
Lesion count ^h	X	X				X	X	X				X				X	X	X		
NRS Patient Glob. Ass. Skin Pain ⁱ	X	_										•	X	X		X	X	X		
PGA		X				X	X	X				X				X	X	X		
Erythema score		X				X	X	X				X				X	X	X		
Photography (opt. substudy) ^j		X					X					X						X		
HS-PGIC		X				X	X	X				X				X	X	X		
HADS	X	X	X	X	X	X	X	X	X	X	X	X	X	X	X	X	X	X	X	
DLQI		X					X					X				X		X		
EQ-5D		X					X					X				X		X		
SF-12		X					X					X				X		X		
Laboratory Tests																				
Serology (HBsAg, HCV)	X																			
TB test ^k	X																			
HIV testing	X																			
Hematology/Chemistry	X	X				X	X	X				X				X		X	X	

																			Follo	ow-up ^b
Procedures	Screen		Treatment Period (weeks) ^a												8 weeks after last dose	14 weeks after last dose/EOS				
	≤ 28 d prior to d1	0 (d1)	1	2	3ª	4	8	12	13ª	14	15ª	16	17ª	18	20	24	28	32 or ET ^p	39	45
Urinalysis	X	X					X	X				X						X	X	
C-reactive protein	X	X				X	X	X				X				X		X		
Fasting lipid (total cholesterol, triglycerides & HDL)	X											X								X
Hemoglobin A1C		X										X						X		
Pregnancy test (WOCBP only) ¹	X	X				X	X	X				X			X	X	X	X	X	
PK sampling ^m		X		X		X	X	X				X				X		X	X	X
ADA sampling ^m		X		X		X	X	X				X				X		X	X	X
Exploratory biomarker sampling ^m		X				X	X					X						X		
Treatment Assignment																				
Treatment assignment/Randomization		X																		
Study drug administration and Diary	d Dosing																			
QW dosing (at site) ^{a, n}		X	X	X	X	X	X	X	X	X	X	X	X		X	X	X			
Q2W dosing (at site) ^{a, n}		X		X		X	X	X		X		X		X	X	X	X			
Dosing diary ^o																		→		

ADA = anti-drug antibody; AE = adverse event; AN = abscess and inflammatory nodule; d = day; CRF = case report form; C-SSRS = Columbia-Suicide Severity Rating Scale; DLQI = Dermatology Life Quality Index; ECG = electrocardiogram; EOS = end of study; EQ-5D = European Quality of Life 5-dimension;

ET = early termination; HADS = Hospital Anxiety and Depression Scale; HBsAg = hepatitis B surface antigen, HCV = hepatitis C virus; HS-PGIC = HS Patient Global Impression of Change; NRS = Numeric Rating Scale; PGA = Physician's Global Assessment; PK = pharmacokinetic; PPD = purified protein derivative; Q2W = every other week; QW = once weekly; SAE = serious adverse event; SF-12 = 12-Item Short Form Survey; TB = tuberculosis; WOCBP = women of childbearing potential.

- ^a Visit/dosing windows of ±3 days on either side of the scheduled visits/dosing are permitted; however, the investigator should try to keep the subjects on the original visit/dosing schedule. In case of a delayed or missed dose, the investigator should return subjects on the original visit/dosing schedule in relation to Day 1 for subsequent doses. The window of ± 3 days is relative to Day 1 and applicable for all subsequent visits/dosing. For QW dosing, the time between doses should be no less than 4 days and no more than 10 days. For Q2W dosing, the time between doses should be no less than 11 days and no more than 17 days. Study visits for QW dosing are not required at Weeks 5 to 7, 9 to 11, 18, 19, 21 to 23,25 to 27, or 29 to 31 if subject/caregiver completes study drug administration at home. Subjects randomized to Q2W arms are not required to complete visits on Weeks 1, 3, 13, 15, and 17. Study visits for Q2W dosing not required at Weeks 6, 10, 22, 26, or 30 if subject/caregiver completes study drug administration at home. See footnotes n and o below.
- ^b The follow-up period consists of 2 visits to be completed by all subjects at Week 39 and Week 45. For subjects who early terminate, the follow-up visits should be completed 8 weeks (± 5 days) and 14 weeks (± 5 days) after the last dose of study drug.
- ^c Vital signs include measurements of temperature, respiratory rate, systolic and diastolic blood pressure, and pulse. Measurements should be taken in a sitting position after 5 minutes of rest.
- d Electrocardiograms in triplicate will be recorded after subject has been supine for at least 5 minutes.
- ^e Chest x-ray (posterior/anterior or anterior/posterior) will be performed at screening for subjects who do not have a chest x-ray available within 3 months of screening. Women of childbearing potential must have negative pregnancy test before x-ray is performed.
- f Serious adverse events will be recorded from the signing of informed consent through the 8-week follow-up visit (ie, 8 weeks after the last dose of study drug); adverse events will be recorded from Day 1 (ie, administration of study drug) until 4 weeks after the last dose of study drug.
- ^g Confirm ongoing antiseptic wash requirement at every visit. From Screening through Week 16, subjects will complete a daily diary of their analgesic use. From Week 16 through Week 32, subjects will be required to tell site staff if they took any analgesics within 24 hours of their site visit. See Section 10.10. Subjects will refrain from taking analgesics 12 hours before the site visit, if possible.
- ^h Lesion count will be performed at every study visit marked in the Schedule of Activities and must address all relevant anatomical regions in each subject. The AN count includes counts of draining tunnels (fistulas and sinuses). See Section 8.1.1 for more details. Any unscheduled visit for disease worsening based on the investigator judgment will include AN count and will be recorded in the appropriate CRF.
- ¹From screening through Week 16, subjects will complete a daily diary of their skin pain. See Section 8.1.5. No in-site assessment of skin pain will be completed at the Week 16 visit. From Week 16 through Week 32, subjects will complete skin pain assessments at the site. Note: subjects may not be randomized if pain diaries are not completed for ≥ 3 out of 7 days (at a minimum) prior to the Day 1 visit.
- ^j For subjects who consent to the optional photography substudy at selected sites, photographs will be taken.
- ^k QuantiFERON® test or PPD test for TB will be performed. Note: T-SPOT® testing may be allowed after consultation with medical monitor.
- ¹Serum pregnancy test required for screening and urine pregnancy test required at all other times for women of childbearing potential.
- ^m Pharmacokinetic and ADA blood sampling will be taken prior to administration of study drug (pre-dose) on dosing days.
- ⁿ Administration of study drug should be done last after all study procedures unless indicated otherwise. Subjects will be monitored at the study site for at least one hour after study drug administrations at the following visits: for subjects enrolled to QW arms, on Day 1 and Weeks 1, 16, and 17; for subjects enrolled to Q2W arms, on Day 1 and Weeks 2, 16, and 18. After Week 4, qualified subjects may perform home dosing of study drug at weeks without study visits (see footnote a) and do not need to return to the clinical site on those weeks. Subjects may begin self-administration of study drug from Week 5 (QW dosing) or Week 6 (Q2W dosing). Subjects will be trained on study drug handling and self-administration of study drug at the study visits prior to beginning self-administration. A subject's caregiver or designee can also be trained on home dosing based on the subject's preference. Study-site staff will administer study drug at the first 2 visits. Thereafter, if home dosing is a consideration, the subject or subject's caregiver or designee must administer and demonstrate competency

for at least 2 visits prior to being allowed to dose at home. Otherwise, the subject will need to return to the site for all injections. The last dose of study drug for subjects dosed QW is Week 31 and for subjects dosed Q2W is Week 30.

[°] A dosing diary will be completed for every home dosing administration.

^p Subjects who end the study early will complete an early termination visit and complete the procedures described at the Week 32 visit within 2 weeks of the last dose of study drug.

2. Introduction

Izokibep is a potent and selective inhibitor of interleukin 17A (IL-17A) that is being developed for treatment of hidradenitis suppurativa (HS).

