2.3.3. Overall Benefit-Risk Conclusion

The following considerations are important for the benefit-risk assessment:

- Only subjects with moderate to severe HS will be enrolled. Subjects must have HS lesions present in at least 2 distinct anatomic areas, one of which is Hurley Stage II or Hurley Stage III and AN count of ≥ 5. However, subjects with draining fistula count of > 20 at screening will be excluded.
- The inclusion and exclusion criteria will ensure that subjects who might be predisposed to a higher risk of drug-related TEAEs are either excluded or identified and treated with caution. Class effects seen with other IL-17 inhibitors have been taken into account when designing the eligibility criteria. Subjects with active infections or with a history of autoimmune, chronic inflammatory, or connective tissue disease will be excluded from participating in the study.
- Subjects will be monitored at the study site for at least one hour after the first 2 study drug administrations of izokibep.
- After enrollment and through the end of the study if the subject's AN count is ≥ 150% of Day 1 AN count, antibiotic rescue medication is permitted.

- In Part B of the study, placebo treatment will be limited to 16 weeks. After Week 16, subjects randomized to placebo will begin blinded active treatment (izokibep 160 mg) in order to potentially derive benefit from the disease-relevant effect of IL-17 inhibition.
- Participation in the trial is voluntary. Each subject may refuse to participate or withdraw
 from the trial, at any time, without penalty or loss of benefits to which the subject is
 otherwise entitled.

Taking into account the measures taken to minimize risk to subjects participating in this study, and the lack of clear dose-limiting AEs associated with izokibep, the pre-existing data on the effects of IL-17 inhibitors in hidradenitis, the potential risks identified in association with izokibep are justified by the anticipated benefits that may be afforded to subjects with HS.

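### After one missed dose at the Week 16 switch, a placebo switcher's second izokibep dose falls outside the observation visits in SoA footnote n, although Section 2.3.3 promises to observe it

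*Protocol*

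**What the plan says.** The commitment is in Protocol Section 2.3.3, among the benefit-risk considerations, and it counts doses of izokibep: "Subjects will be monitored at the study site for at least one hour after the first 2 study drug administrations of izokibep".

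The working instruction is in Section 1.3, footnote n, and it lists visits: "Subjects will be monitored at the study site for at least one hour after study drug administrations at the following visits", namely "for subjects enrolled to QW arms, on Day 1 and Weeks 1, 16, and 17", and "for subjects enrolled to Q2W arms, on Day 1 and Weeks 2, 16, and 18". The same footnote opens home dosing: "After Week 4, qualified subjects may perform home dosing of study drug at weeks without study visits". Self-administration may begin at Week 5 (QW) or Week 6 (Q2W).

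Footnote a covers missed doses: "In case of a delayed or missed dose, the investigator should return subjects on the original visit/dosing schedule". It also names the weeks that need no site visit when the subject doses at home. For QW: "Study visits for QW dosing are not required at Weeks 5 to 7, 9 to 11, 18, 19", with later weeks following. For Q2W: "Study visits for Q2W dosing not required at Weeks 6, 10, 22, 26, or 30". Section 4.1.2 agrees: the QW visit list has no Week 18, while the Q2W list includes Week 20.

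Section 6.1.1 also asks for an hour after the first two administrations, but of study drug, which Section 6 defines to include placebo.

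**The concern.** For Groups 1 and 2 the first izokibep dose is planned for Week 16. A dose-based promise and a week-based instruction agree only while neither of the first two post-switch doses is missed. Once one is missed, the dose moves and the observation hour does not.

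No other procedural text closes the gap for switchers. The Section 6.1.1 rule was used up on placebo at the start of the study. Qualification for home dosing was also gained on placebo. Sites are blinded, so they cannot tell which subjects are receiving izokibep for the first time.

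The stake is a safety procedure. The sponsor chose to observe both doses, and Section 8.3.6 lists systemic hypersensitivity as an event of special interest. Missed doses are foreseen: Section 5.5 has a dose withheld for safety recorded as missed, and SAP Section 6.7 allows for a first Period 2 dose after a missing Week 16 visit. A subject whose dose was withheld for an adverse event could then take the second izokibep dose at home with the schedule followed.

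**Working it through.** **Step 1. Walk the dosing calendar.** Inputs are the post-switch dosing weeks (QW every week from 16; Q2W every second week from 16), the footnote n weeks, the footnote a home-dosing weeks and the Section 4.1.2 visit lists. A dose given within the ±3-day window stays at its listed visit, so only true misses count.

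| Regimen | Missed | 1st izokibep dose | 2nd izokibep dose |
|---|---|---|---|
| QW | none | Week 16, listed | Week 17, listed |
| QW | Week 16 | Week 17, listed | Week 18, not listed, home allowed |
| QW | Week 17 | Week 16, listed | Week 18, not listed, home allowed |
| Q2W | none | Week 16, listed | Week 18, listed |
| Q2W | Week 16 | Week 18, listed | Week 20, on site, no hour listed |
| Q2W | Week 18 | Week 16, listed | Week 20, on site, no hour listed |

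The second dose is covered in 2 of 6 cases, the two with no miss. The first dose is covered in all six. It is uncovered only if both doses are missed and dosing resumes (Weeks 18 and 19 for QW, Weeks 20 and 22 for Q2W).

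**Step 2. Size it.** The plan gives no missed-dose rate or home-dosing uptake, so both are assumed. Let p be the chance of missing each dose, independent between doses. Groups 1 and 2 have 28-29 subjects each, so 56-58 in all; 57 is used, with all assumed to reach Week 16.

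- Chance that a switcher misses at least one of the two doses: 1 − (1 − p)².
- Expected switchers affected: 57 × [1 − (1 − p)²].
- Group 1 share: 28.5 × [1 − (1 − p)²]; multiply by uptake for doses taken at home.
- First dose also uncovered: at most 57 × p².

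| | p = 2% | p = 5% | p = 10% |
|---|---|---|---|
| Misses at least one | 3.96% | 9.75% | 19.0% |
| Switchers affected, of 57 | 2.26 | 5.56 | 10.83 |
| of these, Group 1 (QW) | 1.13 | 2.78 | 5.42 |
| second dose at home, 25% uptake | 0.28 | 0.69 | 1.35 |
| second dose at home, 50% uptake | 0.56 | 1.39 | 2.71 |
| second dose at home, 75% uptake | 0.85 | 2.08 | 4.06 |
| First dose also uncovered | 0.02 | 0.14 | 0.57 |

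**Step 3. Chance that it happens at all.** With 57 × 2 = 114 doses at risk, the chance of at least one affected switcher is 1 − (1 − p)^114: 43.5%, 68.2% and 90.0% at p = 0.5%, 1% and 2%. This includes Q2W subjects, who after a single miss are still on site. For a QW switcher taking the second dose at home at 50% uptake, the chance of at least one is 1 − {1 − 0.5 × [1 − (1 − p)²]}^28.5, or about 13%, 25% and 43% at the same rates.

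**Step 4. Allow for dropout.** If 85% of switchers reach Week 16 (57 × 0.85 = 48.45), the expected numbers affected fall to 1.9, 4.7 and 9.2 at p = 2%, 5% and 10%. The chance of at least one at p = 2% falls to 86%.

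**The case against.** The strongest reply is that Section 2.3.3 is live protocol text and already requires the hour. Footnote n lists visits for the planned course and does not say that observation is unnecessary elsewhere. A blinded site could satisfy both by counting doses from Week 16 in every subject. Section 8 demands adherence to design requirements including those in the SoA, which does not rank the SoA above Section 2.3.3. This stands in part: the safeguard is stated, and the defect is a conflict between two sections. But the footnotes positively allow a qualified QW subject to dose at home at Week 18, and no site instruction says to restart the count at Week 16.

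A second reply is that the early weeks have the same form: a Group 3 subject who misses Week 1 takes the second izokibep dose at Week 2, also off the list. There, however, Section 6.1.1 covers that dose, because the subject started on izokibep. Switchers have no such backing.

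Three limits should be granted:

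- The contingency is narrow. The QW windows around Weeks 16 and 17 are contiguous, so a late attendance generally still falls at a listed visit.
- After a missed Week 17 visit, home dosing at Week 18 needs drug already in hand, and the documents do not say when home supplies are dispensed. A missed Week 16 dose, or a dose withheld at an attended visit, does not have this limit.
- The safety link is precautionary. Section 2.3.1 says that class effects have not been identified with izokibep, while noting small numbers, and nothing in the documents singles out the second dose.

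**Conclusion.** The concern holds as a minor point. Footnote n and Section 2.3.3 agree only when no dose is missed; in all four single-miss cases the second izokibep dose leaves the listed visits. The consequence is heavier for QW, where the dose may be taken at home, than for Q2W, where after a single miss only the listed hour is absent.

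The calendar result needs no assumption. The counts rest on assumed miss rates, independence and home-dosing uptake. Across 2% to 10% missed and 25% to 75% uptake, about 0.3 to 4.1 QW switchers would be expected to take the second dose at home unobserved. Sample size, power, alpha and the efficacy analysis are not affected.

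**What to change.** In footnote n, keep the Day 1 and Week 1 (QW) or Week 2 (Q2W) observation. Replace the fixed post-switch weeks with a dose-based rule for all Part B arms: *at least one hour on site after each of the first two administrations given at or after Week 16, at whichever visit they occur; from Week 16, no home dosing until both have been given on site.* Put matching text in Section 6.1.1. Section 2.3.3 needs no change. Applying the rule to every arm preserves the blind, and the second dose is then observed in all six cases in the table.

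The cost is one sentence in each place, and nothing for subjects who miss neither dose. A Part B subject who misses one needs an on-site dose with an hour's stay at Week 18 (QW) or one extra hour at the existing Week 20 visit (Q2W). At 2%, 5% or 10% missed, 170 × [1 − (1 − p)²] gives about 7, 17 or 32 subjects who miss at least one, of whom about 3, 8 or 16 are among the 85 in the QW arms. An added site visit arises only for QW subjects who would otherwise have dosed at home. If both doses are missed (170 × p² = 0.07, 0.43 or 1.7 subjects), the Week 19 (QW) or Week 22 (Q2W) dose must also be given on site.
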